1.2 Trial Schema

*The process: progression of osteoarthritis is very slow. It will be very unlikely that more than 1 patient wants to change to the operated group within the 5 years of the trial. The same is true for progression to TKA. The possibility to change later in the operated group will take off the pressure from the patient to make the “wrong” decision now.

See point 1.3 Schedule of activities for details.

1.3 Schedule of Activities

Observation parameter in detail:

| Parameter | Screening (EU*) | Enrollment? yes/no | Surgery OP | Follow-up | | | | | |
|---|--------------------|-----------------------|---------------|-----------------|----|----|----|----|----|
| | | | | U1 [#] | U2 | U3 | U4 | U5 | U6 |
| date | V | | V | V | V | V | V | V | V |
| surgeon | V | | V | V | V | V | V | V | V |
| Medical history (age, gender, working status, co-morbidities) | V | | | | | | | | |
| weight | V | | | | | | | | V |
| height | V | | | | | | | | V |
| BMI | V | | | | | | | | V |
| Nicotine | V | | | | | | | | V |
| Side | V | | | | | | | | |
| Previous knee treatment | V | | | | | | | | |
| Cartilage damage | V | | | | | | | | |
| Leg axis misalignment | V | | | | | | | | |
| Properties of the meniscus | V | | | | | | | | |
| Sport | V | | | | | | V | V | V |
| Scores (KOOS, IKDC) | V | | | | | | V | V | V |
| VAS-pain Score | V | | | | | | V | V | V |
| Diagnose | V | | | | | | | | |
| Inclusion criteria | V | V | | | | | | | |
| Exclusion criteria | V | V | | | | | | | |
| Written informed consent | | V | V | V | V | V | V | V | V |
| Pregnancy test | | | V | | | | | | |
| Surgeon | | | V | | | | | | |
| Time of surgery | | | V | | | | | | |
| Graduation after Outerbridge [1] | | | V | | | | | | |
| Way of Fixation | | | V | | | | | | |
| Spongioflex®-properties | | | V | | | | | | |
| Antibiotica | | | V | | | | | | |
| Additional Procedures | | | V | | | | | | |
| Complication | | | V | V | V | V | V | V | V |
| MR-image evaluation | V | | | | V | V | V | V | V |
| Pain at rest | | | | V | V | V | V | V | V |
| Pain when walking | | | | V | V | V | V | V | V |
| Pain at sport | | | | | V | V | V | V | V |
| Pain medication | V | | | V | V | V | V | V | V |
| Reoperation | | | | V | V | V | V | V | V |
| Patient satisfaction | | | | | V | V | V | V | V |

*EU: screening visit; U1: at the end of hospital stay; U2: 6 weeks after surgery (\pm 4 days); U3: 6 months after surgery (\pm 1 months); U4: 12 months after surgery (\pm 1 months), U5: 24 months after surgery (\pm 1 months); U6: 5 years after surgery (\pm 3 months); [#]grey shading: this parameter will only be evaluated when operated

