6 TRIAL INTERVENTION AND CONCOMITANT THERAPY

6.1 Description of Trial Intervention

The investigator-initiated trial is a "low-intervention clinical trial" according to Article 2(3)CTR. It will be conducted in accordance with the "FSA-Kodex" and the joint recommendations of the BfArM and PEI on the planning, conduct and analysis of investigator-initiated trials. The clinical trial will be conducted in compliance with the protocol, with the CTR regulation and with the principles of good clinical practice according to Annex I section D 17 (a) CTR 536/2014.

The IMP is SUB184038, human cancellous bone, auxiliary medicinal product (NIMP) is Cephazolin, 2 gr. one shot just before surgery, IMP and NIMP for the surgical group only.

Fig. 2 example of packaging and labelling.

The IMP can be stored at room temperature (fig. 2). The transplant must be re-hydrated at least 30 min before implantation in physiological injectable solution (Fachinformation point 4.2).

Intervention for the surgery group: As for any surgical procedure, the patient receives an antibiotic shot (NIMP) just before surgery. The patient will be arthroscopically treated via the arthroscopic portal with implantation of a demineralized bone block (IMP: Spongioflex®, appropriate size (DIZG gGmbH, Berlin, Germany)) as a partial meniscus substitute. The block will be adapted to the defect size and secured with 2-4 inside-out sutures (Etidbond 0, Ethicon, Somerville, NJ). No dosing, the IMP has no systemic effect. The surgery (Intervention) will last between 60-90 minutes. The hospital stay is between 2-3 days after surgery. Follow-up visits: at the end of the hospital stay, after 6 weeks, after 6, 12 and 24 months and after 5 years for the operated group.

Non-operated group: no surgical treatment, no antibiotic shot, no visit at the end of the hospital stay, and no visit after 6 weeks. Follow-up visits after 6, 12 and 24 months and after 5 years.

Table 1: Trial interventions

| Trial intervention | Operated group | Non-operated group |
|--|----------------|--------------------|
| screening | yes | yes |
| enrollment | yes | yes |
| In-hospital surgery as summarized above with IMP and NIMP as defined above | yes | no |
| Follow-up includes MRI evaluation and IKDC, KOOS and VAS-pain-Score at each follow-up visit | yes | yes |
| at the end of hospital stay | yes | no |
| After 6 weeks | yes | no |
| After 6 months | yes | yes |
| After 12 months | yes | yes |
| After 24 months | yes | yes |

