7 DISCONTINUATION OF TRIAL INTERVENTION AND PARTICIPANT WITHDRAWAL FROM TRIAL

7.1 Discontinuation of Trial Intervention

7.1.1 Criteria for Permanent Discontinuation of Trial Intervention

This is an orthopedic trial. The surgery is the start point and after the surgery there is no further treatment. There are only follow-up visits, which include an MRI (after 6 weeks, 6, 12, 24 months and 5 years in the operated group and after 24 months and 5 years in the non-operated group) and 3 questionnaires (IKDC and KOOS, CRF).

Criteria for permanent discontinuation for **single patients** from the trial are the following:

- Withdrawal of the informed consent
- lost to follow-up,
- premature death
- progression of osteoarthritis up to TKA
- the patient wishes to change to the operated group after a certain time

When withdrawal of the informed consent, premature death or lost to follow-up occurs, data up to the point will be used. If progression of osteoarthritis up to TKA occurs, the treatment is counted as treatment failure. These patients cannot continue the trial. Data up to the point will be used.

If the patient changes his decision and want to be operated at a later time point, the patient can continue the trial, but will be allocated to the other study arm. Data collected up to this point will be used in the first treatment group and then data will be generated in the second treatment group.

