7.1.2 Temporary Discontinuation or Interruption of Trial Intervention

This is an orthopedic trial. The surgery is the start point and after the surgery there are no treatments. There are only follow-up visits, which include an MRI and 3 questionnaires (IKDC, KOOS, CRF)

If the patient cannot attend a post-surgical visit at the time envisaged it is possible to do the visit later/earlier. For this there are time ranges given which is as follows:

- U1: at the end of hospital stay (only for operated patients)
- U2: 6 weeks after surgery (\pm 4 days, only for operated patients)
- U3: 6 months after surgery (\pm 1 months, for operated patients, for non-operated patients only PROMs)
- U4: 12 months after surgery (\pm 1 months, for operated patients, for non-operated patients only PROMs)
- U5: 24 months after surgery (\pm 1 months)
- U6: 5 years after surgery (\pm 3 months)

If for any reason this time slots cannot be used by the patient e.g. because of a pandemic or another major event, then the next time slot will be used.

Thus, a temporary discontinuation of the trial is not a problem, because no treatment occurs after surgery, but should be avoided.

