9 STATISTICAL CONSIDERATIONS

Data analysis complies with ICH E9 Guideline and ICH E9(R1) Guideline. This clinical trial is to confirm patient safety and efficiency of the procedure.

For this reason, as primary objective PROMs (IKDC, KOOS and VAS-pain score) will be evaluated before surgery/at the beginning of the trial and then starting at 6 months after surgery/beginning of the trial for the operated or non-operated group, respectively. The evaluation will be performed also after 12 and 24 months and after 5 years. A primary analysis will be performed 2 years after surgery/start of the trial.

At the beginning of the trial and prior to operation demographic and baseline data will be collected and summarized for both groups.

For safety, there will be an evaluation of complications, AE, SAE and SUSARs at each follow-up visit (at the end of the hospital stay, after 6 weeks, after 6, 12, 24, months and after 5 years, for the operated group). The number of AE, SAE and SUSARs will be recorded and evaluated at each visit. MRI evaluation starts at the follow-up visit 6 weeks after surgery for the operated group and 24 months after the start of the trial for the non-operated group. The evaluation of the MRI will be performed after a modified graduation of Genovese et al. [32]. Additionally, there will be the meniscal size evaluated and if there is an extrusion of the meniscus and how big the extrusion is. There will be a Kaplan-Meier-time to event curve for both groups regarding progression of osteoarthritis up to TKA. The analysis will be conducted on all participant data after 2 years and after 5 years.

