9.1 Analysis Sets

Full analysis set will be performed.

PROMs:

Change from baseline for the PROMs (IKDC, KOOS, VAS-pain score) for the operated/non-operated group after 6, 12 and 24 months and 5 years and between groups.

Complications, AE, SAE and SUSARs:

The number of complications, AE, SAE and SUSARs will be evaluated at each time point and compared between the groups with Fishers exact test.

MRI evaluation:

Change in MRI evaluated using the Outerbridge [1] graduation, the size of the meniscal defect and the meniscus itself, the MRI signal of the meniscus will be evaluated after a modified score after Genovese et al.[32] and the number of patients with an extrusion and the size of the extrusion.

Patient satisfaction:

Patient satisfaction will be categorized as: very pleased, pleased, not pleased, very unsatisfied and will be evaluated using the Chi-square test.

Progression of osteoarthritis up to TKA:

The number of patients with progression of osteoarthritis up to TKA for both groups will be compared with a Kaplan-Meier time to event curve.

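### The Schedule of Activities collects no KOOS, IKDC or VAS pain at 6 months, although sections 9 and 9.1 plan a 6-month analysis; separately, Table 1 disagrees with other sections on MRI in non-operated patients

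*Protocol*

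**What the plan says.** **PROM collection.** In Protocol 1.3 the knee-score row reads "Scores (KOOS, IKDC) | V | | | | | | V | V | V" and the pain row reads "VAS-pain Score | V | | | | | | V | V | V". The footnote defines the visit codes, among them "U3: 6 months after surgery".

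**PROM analysis and visit content elsewhere.**
- Section 9 evaluates the PROMs at baseline and "then starting at 6 months after surgery/beginning of the trial for the operated or non-operated group", followed by 12 and 24 months and 5 years.
- Section 9.1 plans change from baseline "after 6, 12 and 24 months and 5 years and between groups".
- Section 7.1.2 describes U3 and U4 as "for operated patients, for non-operated patients only PROMs".
- Table 1 in 6.1 has the row "Follow-up includes MRI evaluation and IKDC, KOOS and VAS-pain-Score at each follow-up visit", answered yes for both groups, and lists a 6-month visit for both groups.
- Section 8 refers the reader to 1.2 and 1.3 for the detail of the assessments.

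**MRI in non-operated patients.** The same Table 1 row covers MRI and is answered yes for them. Section 7.1.1 places their MRI "after 24 months and 5 years in the non-operated group". Section 9 starts it at 24 months, 3.2 restricts the 6-week, 6-month and 12-month images to operated patients, and 7.1.2 leaves no MRI in the non-operated 6- and 12-month visits.

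**Primary endpoint.** Sections 1.1 and 3.1 set it at 2 and 5 years.

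**The concern.** The schedule is the list from which a case report form is built and against which a monitor checks visits. Here it omits all three primary instruments at a visit where the statistical section plans to analyse them. A questionnaire not handed out at 6 months cannot be recovered later, and an analysis plan cannot supply data that the schedule never collects.

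Two things depend on it. The first is the 6-month within-group and between-group comparison in 9.1, which 9.2.1 repeats by planning to compare the groups at every time point. The second, on one reading of the missing-data rule in 9.2.2 and 9.2.3, is what remains for a patient who leaves between 6 and 12 months. The MRI disagreement is a separate matter of the same kind: two sets of visits for the same patients.

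**Working it through.** The protocol gives no figure for this point that could be reproduced. The check is a reading of the table and a comparison of sections.

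**1. Is the blank at U3 a broken table?** The header has 10 columns: parameter, screening, enrolment, surgery, U1 to U6. Split at the cell borders, the rows give:

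| Row in 1.3 | Cells | Ticked at |
|---|---|---|
| KOOS, IKDC | 10 | screening, U4, U5, U6 |
| VAS pain | 10 | screening, U4, U5, U6 |
| Sport | 10 | screening, U4, U5, U6 |
| MR image | 10 | screening, U2 to U6 |
| Pain at rest | 10 | U1 to U6 |
| Patient satisfaction | 10 | U2 to U6 |

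Every row has the full number of cells, and other rows are ticked at U3. The gap is therefore in the table itself and is not a shifted column. The grey shading mentioned in the footnote does not survive in the text. It marks items evaluated only in operated patients, so it cannot turn an empty cell into a tick.

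**2. PROM time points after baseline.**

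| Source | 6 mo | 12 mo | 24 mo | 5 y |
|---|---|---|---|---|
| 1.3 (collection) | no | yes | yes | yes |
| 9 and 9.1 (analysis, both groups) | yes | yes | yes | yes |
| 6.1 Table 1 (both groups) | yes | yes | yes | yes |
| 7.1.2 (non-operated) | PROMs only | PROMs only | visit held | visit held |
| 3.1 (primary endpoint) | – | – | yes | yes |

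Section 9.1 analyses 4 time points and 1.3 collects 3, so 4 − 3 = 1 has no scheduled data. This holds for both groups, 30 + 10 = 40 patients. Both primary time points are collected.

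**3. Last observation.** Sections 9.2.2 and 9.2.3 use data up to the event and analyse the last observation. Suppose this means carrying the last score forward. Under 1.3, a patient who attends U3 but not U4 has only the screening score, so the change is 0. With a 6-month score, the same rule would enter the 6-month change, g. Among 30 operated patients, each such case alters the group mean by g/30. The protocol gives no value for g. As an assumed range for KOOS, take g from 0 to the full expected gain in 9.8, 86 − 46 = 40. The shift per patient is then 0/30 = 0 to 40/30 ≈ 1.3 points. This compares two results of the same rule; it does not show that either is the right value at 2 or 5 years. The protocol gives no number of patients lost in this window, so no total can be calculated.

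**4. MRI visits in non-operated patients.** Table 1 gives 4 (6, 12 and 24 months, 5 years). Section 7.1.1 gives 2 (24 months, 5 years), and 3.2, 7.1.2 and 9 agree with it. Both versions include 24 months and 5 years.

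**The case against.** The best defence is that this is a few missing ticks in one table. Sections 6.1, 7.1.2, 9 and 9.1 all call for 6-month PROMs, and 7.1.2 would leave the non-operated 6-month visit empty without them. The case report form is not among the documents and may already include them. Six months belongs to no declared endpoint in section 3. That is fair: it makes the loss conditional on 1.3 being followed and keeps the point modest. It does not remove the contradiction, because section 8 names 1.3 as the detailed source.

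Table 1 is also weak support. Read literally, its row would require the scores at discharge and at 6 weeks in operated patients, which section 9 does not plan. This stands, but the point does not need Table 1: sections 9 and 9.1 are enough. The same loose wording probably explains the MRI disagreement, where one row stands against four sections.

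Four stronger readings are tempting, and the documents do not support them:
- *The primary analysis cannot be done.* It can; screening, U5 and U6 are ticked for all three instruments.
- *Patients lost between 6 and 12 months will be scored as unchanged.* Section 9.2.3 also disclaims assumptions about missing data and does not say how a patient with only a baseline score enters. Zero change is one reading.
- *Up to 8 of 40 patients are affected.* The 20% (0.20 × 40 = 8) is the total loss accepted over the whole trial, and 11.1 expects loss to follow-up below 10% and withdrawal of at most 5%. None of these figures measures loss between two particular visits.
- *The MRI conflict prevents an analysis of the primary variables.* It has no bearing on the PROMs.

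**Conclusion.** The contradiction holds and is in the current text; 13.4 states that the protocol has not been amended. If 1.3 governs collection, as section 8 indicates, the 6-month PROM analysis in 9.1 has no scheduled data in either group: one of four post-baseline time points. The 2- and 5-year PROM analyses, which carry the primary endpoint, are intact.

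The effect through the last-observation rule is conditional on reading that rule as carrying scores forward, and its total size cannot be derived from the documents.

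The MRI disagreement is real but smaller. It leaves unclear whether non-operated patients have two or four follow-up images, and it does not affect the 2- and 5-year comparison between groups.

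Both should be settled before data collection, since 6-month scores cannot be obtained afterwards. Neither threatens the main result.

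**What to change.** Reconcile 1.3 with 6.1, 7.1.2, 9 and 9.1 in one of two ways:
- tick KOOS, IKDC and VAS pain at U3 for both groups; or
- remove the 6-month PROM analysis from 9 and 9.1, and amend 6.1 and the non-operated U3 visit in 7.1.2 to match.

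Reconcile the MRI entry in Table 1 with 3.2, 7.1.1, 7.1.2 and 9. State the PROM and MRI visits for each group once and have the other sections refer to that place. Check the case report form against the result.

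The cost is a text and table correction. The first option adds three self-completed questionnaires at a visit that already takes place; the second adds no patient burden but gives up the 6-month comparison.

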2 INTRODUCTION

2.1 Purpose of Trial

The menisci consist of fibrocartilage. They are partially (laterally more than medially) mobile parts of the joint surfaces and compensate for the incongruence of the femur and tibia. They reduce the joint pressure on the tibial plateau and the femoral condyles and help to stabilize the joint.[2] Due to this biomechanical relevance, the partial loss of the meniscus leads to arthritic changes in the medium and long term.[3-7] Suturing the torn meniscus is increasingly becoming the focus of knee surgery.[8] Degenerative torn menisci have a significantly poorer prognosis with regard to healing than traumatically torn menisci (e.g. meniscus damage associated with a cruciate ligament tear).[9]

Indications for partial meniscus replacement are symptomatic, degenerative, and irreparable damage to the inner and outer meniscus, possibly with early osteoarthritis of the compartments, as well as partial loss of the meniscus in the event of anterior knee instability in young, active patients, in which case simultaneous reconstruction of the anterior cruciate ligament should be performed. A prerequisite for a good clinical result after partial meniscus replacement is a stable knee without malalignment in the coronal plane. Partial meniscus replacement is not suitable in the case of axial deviation and knee instability, patients older than 60 years, advanced chondromalacia and degenerative changes in the affected compartment, an extension deficit of more than 3° compared to the opposite side or a knee flexion of less than 125°. Inflammatory arthritis or synovial inflammation of the knee and a BMI greater than 30 kg/m² are additional exclusion criteria.

Williams et al. 2007[10] could show, that 5 years after partial removal of the medial or lateral meniscus, despite an excellent functional result, 64% of patients showed medial and 33% lateral cartilage damage on MRI. This study highlights the considerable delay with which the symptoms occur despite already detectable arthritic changes.

Englund et al.[11] were able to show in a study that patients developed osteoarthritis significantly more frequently over a period of 30 months if they had meniscus damage than if they did not. Englund et al. [12] detected tibiofemoral osteoarthritis in 27% of patients 15 years after partial meniscus removal compared to 10% in a control group that had not undergone surgery.

In the case of incomplete meniscus loss, where the peripheral rim is sufficiently intact, defect filling is the only way to restore the lost substance and function of the meniscus.[13,14] In the past, an implant made of bovine collagen (Collagen Meniscus Implant (CMI), Stryker) or an artificial meniscus made of polyurethane (Actifit, 2med) was often used. The CMI has been withdrawn from the market by the manufacturer, so that no biological treatment alternative exists.

Schenk et al. [15] were able to show in a recent study for the CMI, consisting of bovine collagen that, despite a significant improvement in pain and function, the CMI is subject to a progressive shrinkage process over time. The studies mentioned above make it clear that partial replacement of the meniscus is necessary if preservation by meniscus suturing is no longer possible to prevent or postpone arthritic changes.

In the investigator-initiated study on which this application is based, a novel implant made from demineralized allogenic human cancellous bone (Spongioflex®, DIZG gGmbH Berlin) is to be implanted into the meniscus defect of the recipient knee. This transplant has sponge-like properties and therefore facilitates the ingrowth of cells from the surrounding meniscus. The IMP (Spongioflex®) is de-calcified and demineralized, it is hard, when dry, but soft when wet. In the knee the conditions are wet, thus it stays soft. It is pliable (Fig1) and can be easily sutured.

Figure 1: Spongioflex®

The manufacturer (DIZG gGmbH) did a study of cell ingrowth on Spongioflex®[16]. They describe that ingrowth of cells on Spongioflex® was observed after 28 days and these cells do not ossify[16].

Scotti et al. [17] summarizes 2013 the knowledge in respect to meniscal repair as follows:

“In the last decade, striving for optimal restoration of meniscal tissue, the orthopedic surgeon’s armamentarium has been enriched by the use of biocompatible meniscus scaffold and meniscal allograft transplantation”[17]. “However, despite promising short-term results, none of the current strategies have demonstrated regeneration of a functional, long-lasting meniscal tissue and re-establishment of a proper knee homeostasis in the meniscectomised knee”[17]. “The rationale for using a cell-free biomaterial to replace part of the meniscus is based on repopulation of the scaffold by the host cells recruited from the synovium and the meniscal remnants, and subsequent tissue ingrowth which renders this approach cell-based after implantation. A mandatory prerequisite is the absence of both knee instability and malalignment”[17].

This section of the paper of Scotti et al.[17] describes exactly the need for a restoration of the meniscus. Furthermore it [17] defines exactly the features of a scaffold:

”A biomaterial used as scaffold for meniscus tissue engineering purposes should present many features. In particular, the ideal meniscal scaffold should be (i) “cell-instructive”, promoting cell differentiation and proliferation if cell-seeded, or cell migration if cell-free; (ii) “biomimetic”, mimicking architecture, tribology and mechanical features of the native meniscus; (iii) resilient and resistant to withstand mechanical forces acting in the joint while cells produce ECM; (iv) biocompatible, not evoking any foreign-body reaction also with its degradation products; (v) slowly biodegradable allowing to be gradually replaced by biologic tissue; (vi) open, with high porosity, allowing diffusion of nutrients and catabolic substances; and (vii) easy to handle, to be sutured and to be implanted by the surgeon”[17].

Pereira et al. [18] describes that a meniscal implant, either for partial or total replacement should.

“provide the biomechanical properties but also the biological features to replace the loss of native tissue. Moreover, these approaches include possibilities for patient-specific implants of correct size and shape”[18].

Spongioflex® fulfills all these demands described by Scotti et al.[17] and Peirera et al.[18] and it can be adapted in size and shape and thus is in the moment the optimal choice for partial meniscal replacement.

Dickerson et al. [19] describes that

“the scaffold must have a high fluid conductance, concomitant with high porosity.... Porosity allows more rapid cell incorporation along the surface and through the thickness of the scaffold, promoting integration with the host tissue.”[19]. “The scaffold must guide cells to regenerate all four zones of the tissue structure”[19].

This is the case of Spongioflex® it is porose and can guide cells. Scotti et al.[17] proposes 2013 to use CMI for partial meniscal regeneration, but this product is retracted from the market by now and they describe already the shrinking of the transplant[17]. Knee stability and an aligned knee are a requisite for the study proposed. Dickerson et al. [19] shows that new fibrocartilage tissue is formed on the demineralized end of the allograft. Results of Credille et al.[20] support these findings. It will not be ossified again[21]. Smith et al. [22] describes that

“demineralized cancellous bone sponges are Food and Drug Administration-approved and commercially available products that have the potential to provide biologic and biomechanical augments for rotator cuff healing. The sponge can act as a scaffold for cellular attachment and proliferation” [22].

Credille et al. [20] showed in a recent publication that a biphasic interpositional cancellous allograft (BioEnthesis; Sparta BioPharma, Inc., Madison, NJ) can be used for rotator cuff repair. The allograft is

“a porous scaffold for endogenous biological factor migration and thus potentially address the lack of enthesis recapitulation at the rotator cuff repair interface... while the demineralized layer supports soft-tissue ingrowth while acting as a “sponge” to hold bone marrow elements at the repair site”[1].

The group around [name] [21] from the Charité has used Spongioflex® for glenoid repair. They describe that the transplant does not calcify again.[21] The glenoid is also no bony structure. They got an ethic vote (EA1/039/18) for using the same product in non-bone structures and could show successful restoration of the glenoid.

Sundar et al.[23] describes that the use demineralized bone matrix increased fibrocartilage when used for augmentation of rotator cuff repair. The used graft (Spongioflex®) provides a scaffold for cell migration of meniscal cells from neighbouring parts of the meniscus. The intended study will show that this kind of allograft is suitable for partial meniscal replacement because it allows cell migration and has enough porosity to allow fluid conductance [24]. As described by Wildemann et al. [25,26] sufficient growth factors are remaining in the demineralized bone matrix (Spongioflex®) to support new fibrocartilage formation. Scotti et al. [17] underlines the importance of growth factors for meniscal regeneration.

In summary from the literature, it can be concluded, that Spongioflex® is an attractive scaffold for partial meniscal repair because it is fully biological, it still has fibrocartilage inductive factors, allows cell migration, fluid conductivity, resists biomechanical forces, does not provoke immunoreactivity, it is adaptable in size and can easily be sutured. Partial meniscus replacement is an established surgical treatment for patients who have undergone partial meniscus removal[13,15,27,28], to lead to the ingrowth of cells and the regeneration of meniscus-like tissue.[29]

The purpose of this investigator-initiated trial is to evaluate whether the novel graft can prevent/reduce the disadvantages of the previously used replacement materials and shows better results than the group of patients, which were not operated. Since there is currently no alternative made of biological material to this product, this investigator-initiated trial is of great medical and economic importance. The otherwise following arthrosis [30] or knee prosthesis implantation (TKA) could be prevented or at least postponed. Initial clinical results are promising [31].

This surgical method contributes to both pain relief and functional improvement of the knee joint. The aim of this investigator-initiated study is to assess whether the novel transplant can prevent/reduce the disadvantages of the replacement materials used to date. As there is currently no alternative made of biological material to this product, the realization of this investigator-initiated study is of great medical and economic importance.

An important and sensitive parameter for assessing the postoperative function of the meniscus is the MRI image[32]. Genovese et al. 2007 were able to show in a categorization/classification which magnetic resonance image can be expected in the case of successful incorporation[32]. Several studies have shown that the known clinical knee scores (Lysholm, IKDC, KOOS, VAS pain) improve significantly after successful ingrowth of the meniscus implant [13,15,27,28,30].

Refer to the Section 1.2, Trial Schema, and Section 1.3, Schedule of Activities, for more information about the trial design.

